5.2.1. Analyses for Binary Endpoints

For binary endpoints we will derive summary percentages and the corresponding descriptive statistics, as appropriate.

5.2.2. Analyses for Continuous Endpoints

Log transformation may be performed for continuous endpoints as appropriate. Voice task data that fail in technical QC will be excluded in analysis as appropriate.

This section provides analysis methods for continuous endpoints in various well to sick, well state, CCI ██████████ analyses. It is organized as follows:

- 5.2.2.1 defines occurrence of new or increased symptoms (symptom onset)
- 5.2.2.2 defines occurrence of recovery phase
- 5.2.2.3 provides methods for well to sick analysis, which covers participant's sickness progression period from symptom onset to before recovery
- 5.2.2.4 provides methods for well state analysis, which covers participant's well state period from study start to before symptom onset (or to study end if no symptom onset is found)
- 5.2.2.5 provides methods for correlation analysis between symptoms and voice features, which uses participant's data from symptom onset to the time before return to well state (the latter of which will be defined in this section)

- CCI [REDACTED]

5.2.2.1. Definition of Occurrence of New or Increased Symptoms

To define the first occurrence of new or increased symptoms for each participant who has no acute symptoms at enrollment, firstly the maximal total symptom score during the first 3 days with available symptom data of the participant is identified (defined as the Initial Symptom Score). The total symptom score is the sum of all the symptom responses per session converted to numeric as described in [Section 5.2.3](#). An observation is defined as the mean of the daily total symptom score across sessions for each compliant day.

Then the first occurrence of new or increased symptoms is defined as the first day after these 3 days when the observed total symptom score is greater than the Initial Symptom Score.

If no greater value in total symptom score is observed after the first 3 days with available symptom data, no occurrence of new or increased symptoms is defined, and the participant is considered as asymptomatic.

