5.1. Hypotheses and Decision Rules

This is an exploratory study primarily intended to collect data to characterize the relationship between symptoms and voice features for participants with acute viral

respiratory illness. The data will be used to quantify changes from well to sick using voice and self-reported symptoms collected with an Electronic diary in symptomatic SARS-CoV-2/influenza virus/RSV positive participants. The hypotheses that voice and self-reported symptoms will change with acute viral respiratory illness will be tested. This data will be used as the basis to build voice and symptom algorithm(s) for detection and monitoring of these illnesses. No decision rules will be made.

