5.2. General Methods

Data will be summarized using descriptive statistics (number of participants (n), mean, median, standard deviation (SD), minimum and maximum, as appropriate) for continuous (or near continuous) variables, and using frequency and percentages for discrete variables.

Participants can complete the Electronic diary multiple times per day, and each time is considered a session. The session with the most compliant voice and symptom data, and the highest quality voice data will be used for that day to compute the summary statistics. All individual sessions will be used for statistical modeling.

P-values will be generated where appropriate and any p-value < 0.10 will be considered statistically significant. Due to the exploratory nature of the study, p-values will not be adjusted for multiplicity. P-values will be rounded to 3 decimal places and therefore presented as 0.xxx; P-values smaller than 0.001 will be reported as '<0.001'.

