5.2.2.2. Definition of Recovery Phase

To define the recovery phase for each participant who has new or increased symptoms (as defined in [Section 5.2.2.1](#)), firstly the maximal total symptom score on or after the first occurrence of new or increased symptoms, as well as the first day on which this maximal total symptom score is reached (defined as the Maximal Score Day), are identified.

Then the beginning of recovery is defined as the first day after the Maximal Score Day when the total symptom score is decreased from the previous day with available symptom data, followed by two more days of non-increasing total symptom scores.

When no beginning of recovery is observed, all days up to the final study day of the participant are considered as before recovery.

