5.2.2.3. Well to Sick Analysis

For continuous endpoints during well to sick, i.e. after first occurrence of new or increased symptoms in participants based on Electronic diary (defined in [Section 5.2.2.1](#)), the change from baseline will be summarized descriptively by day, defining the first occurrence of new or increased symptoms based on Electronic diary as day=1. For the purpose of the well to sick analysis, the baseline is defined as the average of the endpoint values during the 7-day period before the first occurrence of new or increased symptoms. If a participant has no data during these 7 days, the average of the endpoint values for the closest 3 available days prior to these 7 days will be used for the baseline.

The disease progression from well to sick will be modelled monotonically using data only up to the time before recovery, so that the potential recovery phase afterwards is excluded. The time before recovery is defined in [Section 5.2.2.2](#).

To categorize the well to sick progression during this period (from day=1 to the time before recovery), for each endpoint, the change from baseline will be summarized as follows:

- a. The number and percentage of participants who have less than two days of available data for the endpoint during this period.
- b. For each participant who has two or more days of available data for the endpoint during this period, a linear regression of the change from baseline vs. day, without intercept, will be fit. The participants without a statistically significant trend from the model will be categorized as non-responder, and number/percentage will be summarized.
- c. For each participant with a statistically significant trend from the model in b, two measures will be computed: the day at which the first maximum change from baseline value (direction determined by linear fit in b) is reached during the period (defined as Tmax), and the ratio of the maximum change to the Tmax (defined as Growth Rate). The descriptive summary of the two measures for these significantly responding participants will be presented.

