In addition, the well to sick progression period for each endpoint will be modelled monotonically. Firstly, a linear mixed effect model for the change from baseline vs. day will be used, with slope (i.e. without intercept) included as both fixed effects and random effects (to account for participant level variation). The number of participants used by the model, estimate of the slope's fixed effect mean, standard error, 90% CI, and p-value, as well as the variance estimate for its random effect will be presented.

Secondly, for the statistically significant endpoints determined by the linear mixed effect model, a logistic sigmoid growth/Emax model will also be considered for the population model:

$$y_{ij} - a_{i0} = \frac{d - a_{i0}}{1 + \left(\frac{\text{day}_j}{c}\right)^{-b}} + \varepsilon_{ij}$$

where i represents the i th participant, j represents the j th day, a_{i0} is the baseline value for the i th participant, and y_{ij} is the continuous endpoint value modelled as response. Parameters b , c , d represent the Hill slope, the day at which 50% effect is reached, and the asymptotic maximum sick response for the model, respectively, which can have participant level variation.

To facilitate model convergence, the maximum value observed during the period for each participant (direction determined by individual linear fit from b above), \max_i , will be used to substitute parameter d , and a linear mixed effect model of the logit transformed $\log((\max_i - y_{ij})/(y_{ij} - a_{i0}))$ vs $\log(\text{day})$ will be used for the longitudinal changes, with its intercept and slope included as both fixed effects and random effects. The number of participants used by the model, estimates of the fixed effect means, standard errors, 90% CIs, and p-values, as well as the variance estimates for their random effects will be presented. The

back-transformed mean estimates and 90% CIs for the parameters b and c , where $b = -\text{slope}$ and $c = \exp(-\text{intercept/slope})$, will also be presented.

Additional models may also be considered as appropriate, and the models' goodness of fit will be assessed using Akaike/Bayesian information criteria.

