6. ANALYSES AND SUMMARIES

Throughout the analyses, a participant is defined as symptomatic if they report at least one new or increased symptom in the Electronic diary during the course of the study.

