6.1.1. Main Analysis

6.1.1.1. Well to Sick

- Estimator: Primary Estimator E1(Section 2.1.1). This estimator is intended to provide a population level estimate of the well state as well as changes in symptoms and voice features from well to sick in symptomatic SARS-CoV-2, influenza virus, or RSV positive participants using Electronic diary.
- Analysis Sets: (a) Participants in Primary Analysis Set (Section 4) who become SARS-CoV-2, influenza virus or RSV positive (at Swab#2) and symptomatic during the study; (b) A subset of (a) who are symptom free at enrollment; (c) A subset of (a) who have symptoms due to chronic pre-existing conditions at enrollment. These analysis sets will be considered as deemed appropriate by data.
- Intercurrent events and missing data: (a) There are no particular intercurrent events considered. Participants who have events that lead to missing data will be included and missing data will not be imputed. (b) Inadequate compliance – data will be used as recorded.
- Statistical Method: Summary statistics and linear mixed effect analyses as described in Section 5.2.2.3. The total symptom score, each symptom and each voice feature will be modelled individually.
- Summaries:
 - a. Descriptive summaries and corresponding plots of the mean/SD will be provided. For linear mixed effect model analyses, estimates for all parameters fixed effect means, standard errors, 90% CIs, and p-values, as well as the variance estimates for their

random effects will be provided (as described in [Section 5.2.2.3](#)). Results from all models will be presented in a table.

- b. To assess the well-to-sick analysis baseline: For voice features that are determined as statistically significant based on linear model mixed effect analysis, the difference of the voice feature values between every pre-symptomatic day (starting from enrollment day) and the well-to-sick baseline (i.e. 7-day average before symptomatic onset as described in [Section 5.2.2.3](#)) will be computed. The mean/SD of the differences across participants in the analysis set will be plotted by day up to the symptomatic onset.

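### The well-to-sick p-value for symptom scores cannot test whether symptoms change, because onset and window are both chosen from the score under test

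*SAP*

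**What the plan says.** SAP 5.1 states the aim: "The hypotheses that voice and self-reported symptoms will change with acute viral respiratory illness will be tested". SAP 5.2 sets the threshold: "any p-value < 0.10 will be considered statistically significant", without multiplicity adjustment.

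Four definitions in SAP 5.2.2.1–5.2.2.3 produce the test:

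- **Day 1.** The reference is the highest total symptom score over the first three days with data. Onset is "the first day after these 3 days when the observed total symptom score is greater than the Initial Symptom Score". A participant who never exceeds the reference counts as asymptomatic and has no day 1.
- **End of window.** "the beginning of recovery is defined as the first day after the Maximal Score Day when the total symptom score is decreased", provided two further non-increasing days follow. Otherwise the window runs to the final study day.
- **Baseline.** The mean of the seven days before day 1, or of the closest three earlier days if those seven are empty.
- **Test.** A linear mixed model of change from baseline on day, with no intercept and a fixed and a random slope. SAP 6.1.1.1 applies it to the total score, each symptom and each voice feature.

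The significance is then used twice in SAP 5.2.2.3. At group level, "for the statistically significant endpoints determined by the linear mixed effect model, a logistic sigmoid growth/Emax model will also be considered". At participant level, "The participants without a statistically significant trend from the model will be categorized as non-responder", and Tmax and Growth Rate are summarised only for the others.

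On timing, SAP 6.1.1.1 analyses participants "who become SARS-CoV-2, influenza virus or RSV positive (at Swab#2) and symptomatic during the study". SAP 6 counts a participant as symptomatic at any time: "defined as symptomatic if they report at least one new or increased symptom in the Electronic diary during the course of the study". SAP 6.2.4.2a summarises the lag from onset to swab #2, but the lag is not a condition for onset.

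**The concern.** A test of whether a score rises is run on a stretch of diary that was selected because the score rose. A significant symptom slope would then be reported as support for the hypothesis in SAP 5.1, although the same p-value would appear without any illness. It would also open the sigmoid model for that endpoint. The per-participant version decides whose Tmax and Growth Rate are described.

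Separately, because day 1 is found from the score alone, an unrelated rise weeks from the infection can set the baseline and window for both symptoms and voice. Appendix A defines its own sick and well windows. It is touched only through the univariate results that guide feature selection (Appendix A, 4.2.3).

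**Working it through.** **Plan's own figure.** The only figure attached to this test is the 0.10 threshold. The documents give no type I error or power for it, so there is nothing to reproduce. Sidedness is not stated; two-sided is taken, to match the 90% CIs.

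**Step 1: sign of the day-1 change.** Let M be the maximum total score over the first three days with data, T(d) the daily score and B the baseline.

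- Before day 1, every T(d) ≤ M, so B, a mean of such days, satisfies B ≤ M.
- On day 1, T > M by definition.
- Hence T(day 1) − B > 0 for every analysed participant, whatever process generates the scores.

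**Step 2: the slope.** Without an intercept, a participant's least-squares slope is Σ(day × change) / Σ(day²). Day 1 adds a positive term. The window also contains the maximum, at some day t*, which adds t* × (max − B) > 0 and weighs more the later it falls. Days in between can be negative, so an individual slope need not be positive.

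**Step 3: rejection with no illness.** The planned number of cases is 100 (Protocol 9.2). Set A used 56-day complete diaries and four noise models: 1–3 point blips on 1% or 5% of days, Poisson mean 1, and gamma-Poisson mean 2. It ran 200 sets per model, with REML and a t test. Set B was coded independently with 20% of days missing and four other processes: independent normal, autocorrelated normal, sparse 16-item and chronic 16-item. It ran 300 sets per process, with a Wald test.

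| Total score, sets of 100, noise only | Sets with p < 0.10 (nominal 10%) |
|---|---|
| SAP onset and SAP window (A and B) | 100%, slope always positive |
| SAP onset, fixed 7-day window (A) | 100% |
| SAP onset, fixed 14-day window (B) | 99.7–100% |
| Random day 1, SAP recovery rule (A) | 76–100% |
| Neither rule (A) | 7–12% |
| Onset and window taken from another person's scores (B) | 8–12% |
| Onset re-dated to within 7 or 3 days before swab #2 (A; 5% blip and both Poisson models) | 98–100% |

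The day-1 change was positive in 100% of participants in both sets. In set A, sets of 20 rejected in 94–100%, and sets with real illness also gave 100%. Each rule alone inflates the test, so re-dating day 1 does not repair it.

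**Step 4: other outputs.**

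- Single-symptom slopes reject in 71–82% (A) and 59–87% (B).
- Noise-only participants with two or more window days are labelled responders in 7% (1% blips), 27–30% (5% blips) and 47–51% (Poisson models), against a nominal 10%.
- An unrelated voice feature rejects in 8–20% (A, in both directions; positive 4–12%) and 9–15% (B). The highest rates come from the 1% blip model, where 87% of windows last one day.

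**Step 5: timing.** Swab #1 may be taken on Day 2 to 2 + 6 = Day 8 (Protocol 1.3). Onset can fall from diary day 4, so a rise on days 4–7 can precede a negative swab #1. Positives keep the diary to Week 8 (Protocol 8.1.2), so a first rise after a positive Day 42 swab also qualifies.

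For illustration only, assume unrelated 1–2 point rises on 1%, 2% or 5% of well days, swab #2 taken 0–7 days after true onset, and a 14-day illness curve peaking on day 4. The documents give none of these.

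| Unrelated rises swabbed | Windows starting more than 3 days early (1%, 2%, 5%) | Slope, 1% to 5% (true 2.6) |
|---|---|---|
| All | 2%, 3%, 8% | 2.6 to 2.5 |
| Half | 9%, 15%, 32% | 2.4 to 1.8 |
| None | 16%, 27%, 49% | 2.2 to 1.4 |

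Requiring onset within 7 days before swab #2 dates 0–6% of true onsets late (slope 2.4–2.7). A 3-day limit dates 46–53% late, with slope 3.6–3.8, which is (3.6 − 2.6)/2.6 = 38% to (3.8 − 2.6)/2.6 = 46% too steep.

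**The case against.** **The study is exploratory, and its cases are really ill.** SAP 5.1 makes no decision rule, and the analysed set is RT-PCR positive and symptomatic, so a set of pure noise will not occur. This stands and lowers the severity. It does not rescue the p-value, which looks the same with or without illness, while SAP 5.1 still promises a test.

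**The gate does no harm.** For the total score the gate opens either way, so removing it changes nothing there. That is fair. For single symptoms the gate is a miscalibrated filter, and Tmax and Growth Rate still depend on a miscalibrated label. How much bias that label causes has not been quantified.

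**A 90% CI carries the same reading as the p-value.** This is correct unless the report says otherwise, so the label has to say so.

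**The SAP follows the protocol on timing.** The case definition in Protocol 9.2 sets no interval between onset and swab. Symptoms are meant to trigger swab #2 (Protocol 8.1.2), with daily reminders (Protocol 8.1.3). SAP 6.1.1.1 also plots pre-onset days against the baseline for significant voice features, and parts of the SAP are redacted. All of this stands, and it makes the timing point minor. The planned sensitivity analysis in SAP 6.1.2 concerns missing baseline days, not timing.

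**Conclusion.** The main point holds with high confidence: as written, the symptom-score test cannot test the hypothesis in SAP 5.1. The positive day-1 change follows from the definitions alone. The rejection rate of practically 100% at about 100 participants comes from simulation, but it was the same under eight assumed noise processes. The harm is to interpretation and to the two outputs that depend on significance.

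The timing point is secondary. The gap in the visible text is real, its size is unknown, and it may be small if rises are swabbed as instructed.

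A reader might infer more than the documents support:

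- **That the voice tests are circular too.** Voice features set neither onset nor window, and unrelated ones reject at or modestly above the nominal rate.
- **That a reported symptom rise would be false.** The cases are infected and symptomatic; the p-value simply adds no evidence.
- **That every participant's slope is positive.** In the noise runs, 0–10% of individual slopes were zero or negative.
- **That onset will often be misdated.** The frequencies above rest wholly on assumed blip, swabbing and lag rates.

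**What to change.** **Symptom scores (total and single).**

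- Report well-to-sick changes as estimates with 90% CIs, labelled as conditional on an onset and window defined by the score. State that a CI excluding zero is not evidence of change, and give no p-value against zero.
- Do not use significance to gate the sigmoid model or to define responders.
- Report Tmax and Growth Rate for all participants with two or more window days.
- Amend SAP 5.1 to match, and leave the voice tests as planned.

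**Timing.**

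- Keep the main onset rule.
- Give the SAP 6.2.4.2a lag for the positive set as well.
- Add one sensitivity analysis, for symptoms and voice, requiring onset after swab #1 and within 7 days before the positive swab #2. Report how many participants are re-dated and how many have no rise in that gap.
- Do not borrow the 3-day limit from Appendix A, because it dates many true onsets late.

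**Cost.** SAP wording and a little programming, with no new data. A few true onsets will be dated late under the 7-day rule. Endpoint definitions stay, so an amendment is probably not needed. However, Protocol 9.1 and 9.5 mention testing these changes, so the sponsor should confirm this against its own rule on major modifications (Protocol 9.5, SAP 2).

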5.2.2.2. Definition of Recovery Phase

To define the recovery phase for each participant who has new or increased symptoms (as defined in [Section 5.2.2.1](#)), firstly the maximal total symptom score on or after the first occurrence of new or increased symptoms, as well as the first day on which this maximal total symptom score is reached (defined as the Maximal Score Day), are identified.

Then the beginning of recovery is defined as the first day after the Maximal Score Day when the total symptom score is decreased from the previous day with available symptom data, followed by two more days of non-increasing total symptom scores.

When no beginning of recovery is observed, all days up to the final study day of the participant are considered as before recovery.

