5.2.2.5. Correlation Between Symptoms and Voice Features

Change from baseline in symptom, after first occurrence of new or increased symptoms and before return to well state based on Electronic diary, will be modelled using a mixed-effects model with repeated measures (MMRM) with the change from baseline in the voice feature as covariate, day (categorical factor) as fixed effect, and participant as random effect. For the purpose of this analysis, the baseline is defined as the average of the endpoint values during the period up to 7 days before the first occurrence of new or increased symptoms, and the first occurrence of new or increased symptoms at day = 1. The day of return to well state is defined as the first day after the Maximal Score Day (defined in [Section 5.2.2.2](#)) when the total symptom score is less than or equal to the Initial Symptom Score (defined in [Section 5.2.2.1](#)).

Autoregressive AR(1) variance-covariance structure will be used for the MMRM. The estimate of the coefficient for the change in voice feature, its standard error, 90% CI, and p-value will be presented.

Pearson and Spearman rank order correlations between changes in symptoms and voice features will also be computed for each participant across days. These correlations will be summarized across participants. A heatmap plot will also be presented for each of these correlations.

CCI

CCI [REDACTED]

[REDACTED]

[REDACTED]

[REDACTED]

[REDACTED]

[REDACTED]

[REDACTED]

[REDACTED]

[REDACTED]

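### SAP 5.2.2.2 searches for the Maximal Score Day over all remaining follow-up, so a later, strictly higher score keeps a completed recovery inside a window meant to exclude it

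*SAP*

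**What the plan says.** SAP 5.2.2.1 sets onset (day 1) as "the first day after these 3 days when the observed total symptom score is greater than the Initial Symptom Score". SAP 5.2.2.2 then takes "the maximal total symptom score on or after the first occurrence of new or increased symptoms" and fixes "the first day on which this maximal total symptom score is reached (defined as the Maximal Score Day"). It continues: "the beginning of recovery is defined as the first day after the Maximal Score Day when the total symptom score is decreased", followed by two further days without an increase. If no such run is found, "When no beginning of recovery is observed, all days up to the final study day of the participant are considered as before recovery".

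SAP 5.2.2.3 states the purpose of the window. Progression is "modelled monotonically using data only up to the time before recovery, so that the potential recovery phase afterwards is excluded". Within it, each participant gets a no-intercept regression of change from baseline on day. A non-significant trend (p ≥ 0.10 under 5.2) makes the participant a non-responder. Tmax and Growth Rate are computed only for the others.

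SAP 5.2.2.5 ends the correlation window from the same date: "The day of return to well state is defined as the first day after the Maximal Score Day" on which the total score is back at or below the Initial Symptom Score.

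**The concern.** The search for the maximum has no episode boundary, no end date and no link to swab #2. Participants with a positive swab keep the diary to the end of Week 8, so a second illness or an isolated bad day can follow a completed recovery. If that later score is higher than the first peak, the Maximal Score Day moves to it. The first decline and the well days after it then count as time before recovery. That contradicts the aim in 5.2.2.3, and it can happen even when day 1 is the true onset of the confirmed illness.

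The date is derived from the total score but sets the window for the total score, every symptom and every voice feature (SAP 6.1.1.1). It therefore reaches responder status, Tmax, Growth Rate, the mixed-model slope, the participant maximum in the logit-transformed model, and the correlation and MMRM window. The one sensitivity analysis in SAP 6.1.2 concerns sparse baseline data and would not reveal the problem.

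**Working it through.** The documents give no figure to reproduce, so the rules in SAP 5.2.2.1 to 5.2.2.3 and 5.2.2.5 were applied literally to constructed 56-day diaries.

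**Inputs.** From the SAP: the definitions above and the 0.10 level (two-sided assumed). From the Protocol: eight weeks of diary for positive participants. Assumed: Initial Symptom Score 0; illness from Day 15 with total scores 4, 10, 16, 20, 18, 14, 9, 5, 2, 0; all other days 0 unless stated.

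**Formulas.** With baseline 0, slope = Σ(day × score) / Σ(day²); Growth Rate = maximum change / Tmax.

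**Single illness.** The maximum is on Day 18 and recovery starts on Day 19, so the window is days 1 to 4.
- Slope = (1×4 + 2×10 + 3×16 + 4×20) / (1 + 4 + 9 + 16) = 152/30 = 5.07, p = 0.0001.
- Tmax 4; Growth Rate 20/4 = 5.0.
- The score returns to 0 on Day 24, so the correlation window is 9 days.

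**One later score of 21 on Day 45.** Day 45 is day 31 of the episode and becomes the Maximal Score Day, so the window is days 1 to 31.
- The illness contributes 447 to Σ(day × score) and the later day 31×21 = 651. Σ(day²) = 31×32×63/6 = 10,416.
- Slope = 1,098/10,416 = 0.105, p = 0.17: a non-responder.
- Days at or below the initial score: 31 − 9 − 1 = 21. The correlation window is also 31 days, with the same 21 well-level days.

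**Second illness, 6, 15, 24, 18, 10, 4 on Days 43 to 48.**
- Slope = (447 + 29×6 + 30×15 + 31×24)/10,416 = 1,815/10,416 = 0.174, p = 0.034: still a responder.
- Tmax 31; Growth Rate 24/31 = 0.77.

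| Later event | Window (days) | Of which at or below initial score | Slope | p | Result under 5.2.2.3 |
|---|---|---|---|---|---|
| None | 4 | 0 | 5.07 | 0.0001 | Tmax 4, Growth Rate 5.0 |
| 20 on Day 45 (tie) | 4 | 0 | 5.07 | 0.0001 | unchanged |
| 12 on Day 45 (lower) | 4 | 0 | 5.07 | 0.0001 | unchanged |
| 21 on Day 45 | 31 | 21 | 0.105 | 0.17 | non-responder |
| Second illness, peak 24 | 31 | 19 | 0.174 | 0.034 | Tmax 31, Growth Rate 0.77 |
| 21 on Day 55 | 42 | 32 | 0.051 | 0.22 | non-responder |

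In the last row too few days remain to confirm recovery, so the fallback runs the window to the final study day.

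**Frequency, illustrative only.** Two simulations took day 1 as correct and assumed 2–10% stray days scoring 1–4 and a second illness in 0–10%; they differed in illness shape. Windows crossing a full return to the initial score made up 7–20% and 8–29% for a mean peak of 4, 0.5–6.5% and 0.7–6.6% for a mean peak of 8, and 0–5% and 0–4.6% for a mean peak of 15.

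**The case against.** **Frequency rests on assumption.** This stands. No stray-day rate, peak distribution or second-illness rate is in the documents. Under SAP 5.2.3 the total score can reach 4 + 15×7 = 109 (16 symptoms), so the simulated mean peaks sit low in the range. At a mean peak of 15 with no second illness there were no crossings at all.

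**The consequence is limited.** This stands in part. The study is exploratory, sets no decision rules and allows additional models, and the primary sick window in Appendix A has its own definition around swab #2. But the affected windows serve the main analyses of both primary endpoints.

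**An unbounded maximum protects against a false onset.** This stands and shapes the fix. Any small early rise sets day 1 under 5.2.2.1. With a one-point score on Day 5 before the illness above, the current rule still finds the peak on Day 18. Stopping at the first return after day 1 leaves a one-day window holding only the stray score.

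**Stronger readings the documents do not support.** A reader might infer that any later illness or stray day stretches the window. It does not: because the first day at the maximum is taken, ties and lower scores change nothing. A reader might also infer that a mild case (peak 4 on day 3, recovered by day 8, a single 5 on day 25) would report Tmax 25 and Growth Rate 5/25 = 0.2. With plausible paths between those points the no-intercept fit gives p of about 0.14, so that participant is a non-responder and yields neither figure.

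**Conclusion.** The point holds as a contradiction between the window rule in 5.2.2.2 and its stated purpose in 5.2.2.3, carried into 5.2.2.5. It requires a full recovery followed by a strictly higher total score. The slope is then flattened. The participant either becomes a non-responder or, where the trend stays significant, reports an inflated Tmax and a lowered Growth Rate.

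For one affected participant the effect is large: a 4-day window becomes 31 days or more in the constructed diaries. Across the study it is uncertain. Under the assumed rates it affects from none to about 7% of participants with moderate or severe illness, and more with mild illness. The average slope moves little even in mild illness (1.67–1.91 instead of 1.90–1.96 in one of the simulations). The main harm is to responder status, Tmax and the make-up of the windows. It should be corrected, but nothing here shows that the primary results would be overturned.

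**What to change.** In SAP 5.2.2.2, end the search for the Maximal Score Day on the day before the first day after the positive swab #2 on which the total score is at or below the Initial Symptom Score. SAP 5.2.2.5 already uses that threshold; two consecutive such days may be required. Define recovery and return to well from that maximum, and report how many windows change.

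With swab #2 assumed on Day 17, this restores the single-illness result in each affected diary above: a 4-day progression window and a 9-day correlation window.

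Do not end the search at the first return after day 1. In a simulation with 2% early stray days that rule placed the peak inside the real illness in about 70% of cases, against 79–100% under the current rule. The version tied to swab #2 did at least as well as the current rule in every scenario run.

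The cost is one sentence and one reprogrammed date, with no new data. The downside is that an illness that dips to the initial score soon after swab #2 is cut short. Well days between a stray day 1 and the confirmed illness are a separate onset problem that this change leaves in place: in the Day 5 example the window stays at 14 days, 9 of them at or below the initial score.
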